1. Efficacy (Average Wear Time): Subjects wearing the JJVCI Investigational Test contact lenses on a daily wear basis report an average daily wear time that is statistically no different to that of subjects wearing ACUVUE® OASYS® contact lenses on a daily wear basis. The assessments will be made at the 2-, 4-, 8- and 12-week follow-up visits.
2. Safety (Symptoms): Subjects wearing the JJVCI Investigational Test contact lenses on a daily wear basis have a percentage of reported symptoms, problems, or complaints (Yes or No) that is statistically no different to that of subjects wearing ACUVUE® OASYS® contact lenses on a daily wear basis. The assessments will be made at each follow-up visit.

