1.4. Statistical Hypotheses for Study Objectives

This is a feasibility study and all the following hypotheses are exploratory in nature. Further analysis may be considered at the discretion of the Study Responsible Clinician.

1.4.1. Primary Hypotheses:

Efficacy

- The Test lens [REDACTED] will be significantly lower than the Control lens (ACUVUE® OASYS®), with respect to Eyestrain caused by glare score. The assessments will be made at the 2-, 4-, 8- and 12-week follow-up visits.
- The Test lens [REDACTED] will be statistically no different than the Control lens (ACUVUE® OASYS®) with respect to distance monocular LogMAR visual acuity. The assessments will be made at the 2-, 4-, 8- and 12-week follow-up visits.

Safety

- The Test lens [REDACTED] will be statistically no different than the Control lens (ACUVUE® OASYS®) with respect to percentage of eyes with grade 3 or higher slit lamp findings (Biomicroscopy). The assessments will be made at each follow-up visit.

1.4.2. Secondary Hypotheses:

Efficacy

- The Test lens [REDACTED] will be statistically no different than the Control lens (ACUVUE® OASYS®) with respect to average wearing time. The assessments will be made at the 2-, 4-, 8- and 12-week follow-up visits.

Safety

- The Test lens [REDACTED] will be statistically no different than the Control lens (ACUVUE® OASYS®) with respect to the percentage of reported symptoms, problems or complaints (yes/no). The assessments will be made at each follow-up visit.

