1.5. Sample Size Justification

The plan is to enroll 60 eligible subjects per arm with a target completion of 50 subjects per arm. This is a feasibility study and the sample size was not based on any empirical calculation. A statistical power analysis is provided below for different scenarios of size effects.

The power analysis was based on historical data from 3 double masked randomized 2x2 Crossover bilateral multi-site studies [REDACTED] and [REDACTED]. Since this study is a 2-arm parallel study only data from the first period was used from each of the historical studies in the summary below. There is not a historical study available with the same design and lenses, therefore [REDACTED] and [REDACTED] were chosen since both studies contain the Test lens [REDACTED]. The study [REDACTED] was chosen since it contains the Control lens ACUVUE® OASYS®. In all three studies lenses were worn as a daily wear for approximately 2-weeks each. The follow-up visits occurred approximately at 1- and 2-weeks after the

initial visit. Out of 89 subjects enrolled in [REDACTED] 84 (94.4%) completed the study, 4 (4.5%) discontinued and 1 (1.1%) was enrolled but not dispensed (screen failure). Similarly, out of 71 subjects enrolled in [REDACTED] 67 (94.4%) subjects completed the study, and 2 (2.8%) discontinued and 2(2.8%) was enrolled but not dispensed. Lastly, out of 109 subjects enrolled in [REDACTED] 100 (91.7%) completed the study, 6 (5.5%) subjects were discontinued and 3 (2.8%) subjects were enrolled not dispensed. Of all 263 subjects who were dispensed in the studies, 185 (70.3%) were female and 78 (29.7%) were male. The ages of subjects ranged from 18 to 40 years with an average age of 29 years. Table 1 summarizes the primary endpoints data pooled from the three studies for the first period only.

Table 1: Summary of the primary endpoints data pooled from [REDACTED] and [REDACTED] Period 1 Only

SLF Grade 2	Visits			
	1-Week		2-Week	
	Test	Control	Test	Control
Corneal Edema	0(0.0)	0(0.0)	0(0.0)	0(0.0)
Conjunctival Injection	1(0.6)	0(0.0)	1(0.6)	0(0.0)
Tarsal Abnormalities	2(1.2)	11(10.7)	4(2.6)	9(9.0)
Corneal Neovascularization	0(0.0)	18(17.6)	0(0.0)	14(14.0)
Corneal Staining	0(0.0)	1(0.5)	0(0.0)	0(0.0)
Other Findings	0(0.0)	0(0.0)	0(0.0)	0(0.0)
Total Eyes (N)	154	102	150	100
Any SL Grade 2 ^b	3(1.9)	30(29.4)	5(3.3)	23(23.0)
Any SLF Grade 3+	0(0.0)	0(0.0)	0(0.0)	0(0.0)
Total Unique Eyes	154	102	150	100
Total Unique Subjects	77	51	75	50

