5. EFFICACY

5.1. Analysis Specifications

5.1.1. Level of Significance

All planned analysis for this study will be conducted with a two-sided type I error rate of 5% for primary and secondary hypotheses. Adjustment for multiple comparisons across time will be performed using Bonferroni's method. Both adjusted and unadjusted results will be reported.

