AWT (in hours) will be analyzed using a linear mixed model to test for difference between the Test and the Control groups. Lens Group, Time (2-, 4-, 8- and 12-week), and the interaction between lens and time will be included as fixed effects in the model; and site as random effect. The covariance between residuals from the same subject at different time points will be selected based on the finite-sample corrected Akaike's Information Criterion. Covariance structures considered include homogenous compound symmetry (CS), heterogeneous Compound symmetry (CSH), Spatial Power (SP (POW)), Ante-dependence (ANTE (1)) and unstructured (UN). For ANTE (1) and SP (POW) structures, site and subject will be included as random effects. For the remaining structures only site will be included as random effect. The covariance structure that returns the lowest AICC will be selected as the structure that best fit the data. Heterogeneous residuals covariance structures (R-side) across lens groups will be considered when appropriate. The log-likelihood ratio test will be used to test for the homogeneity between the residual covariance structures. The Kenward and Roger method will be used for the denominator degree of freedom.

Comparison between the Test and the Control groups will be conducted at each time point using a t-test on least square means from the repeated measure analysis. Adjustment for multiple comparisons across time (2-, 4-, 8- and 12-weeks) will be performed using Bonferroni's method with alpha equal to 0.0125(0.05/4). The corresponding simultaneous confidence intervals of least-square means differences will be calculated with 98.75% confidence. Unadjusted multiple comparisons will be calculated with 95% confidence for each comparison.

Eyestrain caused by glare score

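### Average wear time is hypothesised to be 'no different', but the SAP provides only tests of zero difference, with no margin in hours and no rule for reading the intervals, so non-significance is the only available support

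*SAP*

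**What the plan says.** SAP 1.4.2 states that the Test lens "will be statistically no different than the Control lens (ACUVUE® OASYS®) with respect to average wearing time", assessed at weeks 2, 4, 8 and 12. Protocol 4.1.4 says the same from the subject's side: those wearing the Test lens "report an average daily wear time that is statistically no different to that of subjects wearing" the Control lens.

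For the analysis, SAP 5.2.2 says "AWT (in hours) will be analyzed using a linear mixed model to test for difference between the Test and the Control groups". Lens group, time and their interaction are fixed effects, and the arms are compared at each visit by a t-test on least-squares means. Two levels are planned:

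- Adjusted: Bonferroni over four visits, alpha 0.0125. "The corresponding simultaneous confidence intervals of least-square means differences will be calculated with 98.75% confidence".
- Unadjusted: "Unadjusted multiple comparisons will be calculated with 95% confidence for each comparison".

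SAP 5.1.1 sets the frame: "All planned analysis for this study will be conducted with a two-sided type I error rate of 5% for primary and secondary hypotheses".

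Protocol 9.1 has the same structure at 0.01 over five visits with 99% intervals. SAP 1.1 says that the SAP supersedes protocol section 9 where they differ, so 0.0125 governs.

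On size, SAP 1.5 says "The plan is to enroll 60 eligible subjects per arm with a target completion of 50 subjects per arm". Its power tables cover slit lamp findings and visual acuity. Wear time has no SD, effect size or power figure.

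**The concern.** The hypothesis is one of similarity, but the test takes zero difference as its null. Rejecting that null contradicts the hypothesis. Failing to reject it only shows that the data did not separate the arms, which can happen because the lenses perform alike or because wear time is variable and the trial is small.

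To affirm similarity, the interval has to be compared with a stated number of hours. Neither document has such a number, a shifted null or an interval rule. Under the plan, noisier reports and fewer completers make the hoped-for result more likely.

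The multiplicity adjustment pulls the same way. Going from 0.05 to 0.0125 protects against a false claim of difference, but here it enlarges the region in which no difference is found.

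At stake is a report that describes wear time as no different when the data are compatible with a loss that wearers would notice.

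**Working it through.** **Plan's own figures.** 0.05/4 = 0.0125 and 1 − 0.0125 = 98.75%. Both reproduce. There is no wear-time power figure to reproduce.

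**Inputs from the documents.** 50 completers per arm (SAP 1.5; the efficacy set in SAP 2.2.1 is per-protocol completers), 1:1 allocation, two-sided testing at 0.0125 and 0.05, four visits.

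**Assumed inputs.** True loss of 1.0 h/day, constant over visits; SD 1.0 to 3.0 h; between-visit correlation 0.5 to 0.9.

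**Single visit.** Each visit is treated as a two-sample t-test with 98 degrees of freedom.

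- SE = SD × √(2/50) = 0.2 × SD
- Non-centrality = 1.0/SE
- P(non-significant) = P(|T| < critical t), with T a non-central t; critical t is 2.545 at 0.0125 and 1.984 at 0.05
- Half-width = critical t × SE

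For SD 2 h: SE = 0.40 h and non-centrality = 2.5. P(non-significant) is 51.5% at 0.0125 and 30.3% at 0.05. The half-widths are 2.545 × 0.40 = 1.02 h and 1.984 × 0.40 = 0.79 h.

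**All four visits.** Four correlated normal test statistics with the same mean were simulated, counting trials in which none is significant. The ranges below run from correlation 0.5 to 0.9.

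| SD (h) | One visit, 0.0125 | One visit, 0.05 | All four, 0.0125 | All four, 0.05 | Half-width 98.75% / 95% (h) |
|---|---|---|---|---|---|
| 1.0 | 0.8% | 0.1% | under 1% | under 1% | 0.51 / 0.40 |
| 1.5 | 22% | 9% | 3–12% | 1–4% | 0.76 / 0.60 |
| 2.0 | 52% | 30% | 20–37% | 7–19% | 1.02 / 0.79 |
| 2.5 | 70% | 49% | 40–57% | 19–35% | 1.27 / 0.99 |
| 3.0 | 80% | 62% | 55–70% | 31–49% | 1.53 / 1.19 |

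The all-four columns matter most if the hypothesis is read as holding at every visit. The single-visit miss reaches 50% at an SD of about 2.0 h (0.0125) or 2.55 h (0.05).

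**What the interval adds.** Suppose SD 2 h and an observed difference of −0.5 h. The 95% interval is −0.5 ± 0.79, or −1.29 to +0.29 h. The p-value is non-significant, yet the interval shows that a loss of 1 h is not excluded.

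**What a margin would cost.** Take an illustrative rule that the lower 95% limit must lie above −1.0 h. Truly equal lenses pass one visit 91%, 70%, 51% and 38% of the time for SD 1.5, 2, 2.5 and 3 h. They pass all four visits about 77–86%, 42–59%, 21–38% and 12–26% of the time. A true loss of 1.0 h passes a given visit 2.5% of the time.

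**The case against.** Four points can be made for the plan.

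- **It is a pilot.** Protocol 3.1 and SAP 1.4 call all hypotheses exploratory, and the sample size rests on no calculation. A missing power statement for a secondary endpoint is unremarkable here. This stands, and it lowers the severity. It does not make non-significance evidence of similarity, and the SAP does attach an alpha and a multiplicity adjustment to this hypothesis.
- **0.0125 is not the only level.** Correct: unadjusted 95% comparisons are reported too. They are also tests of zero difference without a bound, so the gap remains at both levels.
- **No sentence says that p > 0.0125 will be declared similarity.** Also correct. That is an inference from the hypothesis wording and from the absence of any other criterion.
- **The estimates and intervals are already planned.** This is the best defence. A careful reader could see which losses are not excluded, so it would be too strong to say that the trial cannot inform the wear-time question. What is missing is a statement that the conclusion comes from the interval.

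A reader might also infer that a real loss of about an hour a day would often pass as no difference. The documents do not support that, because they give no SD for wear time. It holds for a single visit if the SD is about 2 h or more, is weak at 1.5 h and fails at 1.0 h. Over all four visits it is less likely still.

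**Conclusion.** The mismatch stands on the text alone and needs no assumption: a similarity hypothesis, zero-difference tests at two levels, no margin in hours and no rule for the intervals. At any SD the plan has no criterion that can affirm its wear-time hypothesis, and the Bonferroni step favours the non-significant outcome.

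The practical size is conditional. For a true loss of 1.0 h/day with 50 per arm, the chance that all four visits are non-significant at 0.0125 runs from under 1% (SD 1.0 h) to 55–70% (SD 3 h). At 0.05 it runs from under 1% to 31–49%. The loss, the SDs and the correlations are all assumed. Severity is low: one exploratory secondary hypothesis in a feasibility study, with the needed estimates already in the planned output.

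**What to change.** In SAP 5.2.2 (Average Wear Time), state that the conclusion rests on the Test minus Control least-squares mean difference with its unadjusted 95% interval at each of weeks 2, 4, 8 and 12. Describe each interval by the losses and gains in hours that it does and does not exclude. Add that 'no different' will not be concluded from p > 0.0125 or p > 0.05. Reword SAP 1.4.2 and Protocol 4.1.4 to match.

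If the sponsor wants a formal claim of similarity, or of wear time not being reduced, it should fix and justify a margin in hours before database lock. The unadjusted 95% interval is then judged against that margin. No Bonferroni step is needed where the claim must hold at every visit. If the margin is not met, the result is reported as inconclusive.

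The cost is wording only; model, data and sample size do not change. The drawback is that the wear-time result may be inconclusive. With the illustrative 1.0 h margin at all four visits, that would be the usual outcome even for truly equal lenses at an SD of 2.5 h or more, which is a reason to prefer plain interval reporting in a pilot.

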4.4.2 OPTIONAL FLOWCHART

4.5 RANDOMIZATION AND MASKING

Subjects will be randomly assigned to either JJVCI Investigational Contact Lens (Test) or ACUVUE OASYS (Control) groups based on a computer-generated randomization schedule prepared before the study by the sponsor Biostatistician. The randomization will be stratified by study site and randomly permuted blocks of 4 assignments will be used to achieve 1:1 Test versus Control lens type ratio within each study site.

The study site must follow the randomization scheme provided and complete enrollment according to the randomization list and not pre-select or assign subjects. The randomized assignment of subjects will be performed at the first visit prior to the first fitting. The following must have occurred prior to randomization:

- Informed consent has been obtained
- Subject meets all the inclusion / exclusion criteria
- Subject history and baseline information has been collected

This is a partially subject masked study. The dynamic nature (variable shade) of the Test lens makes full masking impossible. However, the identity of the Control lenses will be masked to the subject by way of investigational foil. This will reduce the likelihood that habitual wearers of ACUVUE OASYS recognize the Control lens and increase the likelihood that questionnaires will be answered unbiasedly.

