4.7 DETAILED STUDY PROCEDURES

4.7.1 SEQUENCE OF EVENTS

Habitual Subjects must enter the study wearing their habitual hydrogel lenses for the purposes of accurately responding to the Baseline Questionnaires.

VISIT 1: SCREENING		Day 0
The following information will be recorded:		
Step	Details	
1	Statement of Informed Consent Each subject must read, understand and sign the Statement of Informed Consent before being enrolled in the study (attached separately). A witness must also sign the form. Note: The subject must be provided with a signed copy of this document.	
2	Demographics Date of birth, gender, race, ethnicity, and global ID.	

VISIT 1: SCREENING		Day 0	
The following information will be recorded:			
Step	Details		
3	Case History	Questions regarding the subject's general health and medical history, including concomitant medications. Habitual medications taken by successful soft contact lens wearers are considered acceptable. Note that habitual medications should be continued throughout the study period.	
4	Habitual Contact Lens Type	Questions regarding the subject's habitual contact lens, including: lens name, base curve, diameter, power, and lens wearing modality.	
5	Current Contact Lens Wear Times	Record the habitual wear time (WT) and comfortable wear time (CWT).	
6	Eligibility at Screening	All responses to Inclusion Criteria questions must be answered "yes," and all responses to Exclusion Criteria questions must be answered "no" for the subject to be considered eligible.	

VISIT 1: BASELINE INFORMATION		Day 0	
The following information will be recorded:			
Step	Details		
1	Spherical Over-refraction	Perform a spherical over-refraction OD and OS. The over-refraction of their habitual lenses must be within ± 0.25 D OD and OS. Subjects outside of this range will not be allowed to participate in the study.	
2	Glare Questionnaire	The subject will respond to the Eyestrain Caused by Glare Questionnaire in regards to their habitual lenses.	
3	Project-Specific Questionnaire	The subject will respond to the Project-Specific Questionnaire	
4	CLUE Baseline Questionnaire	The subject will respond to the CLUE Baseline Questionnaire	
5	GSI Background Questionnaire	The subject will respond to the GSI Background Questionnaire	
6	Activity History Questionnaire	The subject will respond to the Activity History Questionnaire	

VISIT 1: BASELINE INFORMATION		Day 0
The following information will be recorded:		
Step	Details	

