2.2. Analysis Sets

2.2.1. Efficacy Analysis Set

Efficacy analyses will be performed on all randomized subjects who completed the study and did not substantially deviate from the protocol as determined by the trial cohort review committee prior to database hard lock (Per-protocol population). Justification of excluding subjects with protocol deviations in the analysis population will be documented in a memo to file. Additional post-hoc analyses may be conducted by including all randomized subjects who have been successfully dispensed and have at least one follow-up visit (i.e. all available data).

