2.3. Definition of Subgroups

Iris color information will be collected (Hue, and Lightness of iris) in order to categorize subjects into two groups “Dark” and “Light” iris to allow for comparisons within iris categories.

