Eyestrain items will be scored using item response theory. A lower score indicates less eyestrain, whereas higher score indicates more eyestrain. Eyestrain score will be analyzed using a linear mixed model to test for difference between the Test and the Control groups. Lens Group, time (2-, 4-, 8- and 12-week), iris category and all interactions between lens group, time and iris category will be included as fixed effects in the model; and site as random effect. The covariance between residuals from the same subject at different time points will be selected based on the finite-sample corrected Akaike's Information Criterion. Covariance structures considered include homogenous compound symmetry (CS), heterogeneous Compound symmetry (CSH), Spatial Power (SP (POW)), Ante-dependence (ANTE (1)) and unstructured (UN). For ANTE (1) and SP (POW) structures, site and subject will be included as random effects. For the remaining structures only site will be included as random effect. The covariance structure that returns the lowest AICC will be selected as the structure that best fit the data. Heterogeneous residuals covariance structures (R-side) across lens groups will be considered when appropriate. The log-likelihood ratio test will be used to test for the homogeneity between the residual covariance structures. The Kenward and Roger method will be used for the denominator degree of freedom.

If the interaction between lens and iris category is significant at the 15% significance level, then comparison between lenses within each iris category will be conducted. If the interaction between lens, iris category and time is significant at the 15% significance level, then comparison between lenses within each iris category at each timepoint will be conducted.

Comparison between the Test and the Control groups will be conducted at each time point using a t-test on least-square means from the repeated measure analysis. Adjustment for multiple comparisons across time will be performed using Bonferroni's method with alpha equal to 0.0125 (0.05/4). The corresponding simultaneous confidence intervals of least-square means differences will be calculated with 98.75% confidence. Unadjusted multiple comparisons will be calculated with 95% confidence for each comparison.

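### The eyestrain and wear-time models leave out the pre-randomization Visit 1 value of the outcome, which costs precision if baseline and follow-up correlate

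*SAP*

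**What the plan says.** **Collection.** Protocol 4.7.1 gives the baseline eyestrain assessment as step 2 of the Visit 1 baseline list: "The subject will respond to the Eyestrain Caused by Glare Questionnaire in regards to their habitual lenses". The questionnaire of the same name is repeated at every follow-up visit. Habitual wear time is recorded at Visit 1 screening, step 5.

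**Timing.** Protocol 4.5 and SAP 1.6 list conditions that must be met before a subject is randomized. One is: "Subject history and baseline information has been collected". Assignment then takes place before the first fitting, so both values precede randomization.

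**Models (SAP 5.2.2).** For eyestrain: "Lens Group, time (2-, 4-, 8- and 12-week), iris category and all interactions between lens group, time and iris category will be included", with site random. For wear time: "Lens Group, Time (2-, 4-, 8- and 12-week), and the interaction between lens and time will be included as fixed effects", again with site random. In both models time begins at week 2, so the Visit 1 value is not a time-zero response either, and no change score is planned. The adjusted results promised in SAP 5.1.1 are adjusted for multiple comparisons across time, not for covariates. The wear-time model in Protocol 9.1 also omits the baseline value, and that section has no eyestrain model.

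**Test.** For eyestrain: "Comparison between the Test and the Control groups will be conducted at each time point using a t-test on least-square means". The wear-time test is of the same kind. Both use a Bonferroni alpha of 0.0125 per visit.

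**The concern.** The lens comparison at each visit is between different people. The repeated-measures covariance structure describes how one subject's visits relate to each other. It does not take stable differences between subjects out of a parallel-group contrast at a given visit, so people who tend to report more glare strain, or to wear lenses longer, add to the error. A pre-randomization measurement of the same outcome can remove the part of that variation it predicts. The trial collects one for both endpoints and does not use it.

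Eyestrain is where this matters most. It is co-primary, and it is the only hypothesis that claims a difference in favour of the Test lens; the others state that the lenses do not differ. SAP 1.5 gives power only for slit lamp findings and visual acuity, and SAP 3 says that eyestrain data are being collected here for the first time. A precise estimate of the eyestrain difference is therefore among the main things a feasibility study of this kind can deliver. For wear time the gain would be a narrower interval.

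**Working it through.** **Inputs from the documents**
- 50 completers per arm, 1:1 allocation (SAP 1.5, 1.6).
- Four visits, two-sided 5% overall (SAP 5.1.1, 5.2.2). The plan's own figure reproduces: 0.05/4 = 0.0125, hence 98.75% intervals.

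**Assumptions, because the documents give no values**
- r, the partial correlation of baseline with follow-up after the other model terms: 0 to 0.7, equal in both arms.
- Eyestrain difference: 0.5 SD, with SD taken within iris group and site.
- Iris split. SAP 2.3 says only "Iris color information will be collected (Hue, and Lightness of iris) in order to categorize subjects into two groups" and gives no proportions.
- One visit with complete data and about 96 df. The Kenward-Roger df will differ.

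**Step 1: standard error of the lens difference at a visit.** With share p in one iris group and the two groups weighted equally:

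SE = sqrt(0.25 × (2/(50p) + 2/(50(1−p)))) = 0.200, 0.218, 0.250 SD at p = 0.5, 0.7, 0.8.

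If iris groups are weighted by observed size, SE stays at 0.200. The SAP does not state the weights.

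**Step 2: half-width of the 98.75% interval without baseline.** t(0.99375, 96) = 2.546, so 2.546 × 0.200 = 0.509 SD. At 70/30 and 80/20 it is 0.556 and 0.636 SD. The wear-time model has no iris terms, and its half-width is about 0.509 SD.

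**Step 3: half-width with the baseline covariate.**

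t(0.99375, 95) × SE × sqrt(1−r²) × sqrt(1 + 1/94)

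The last factor is the cost of estimating the covariate. At r = 0.5 with an even split: 2.546 × 0.200 × 0.866 × 1.0053 = 0.443 SD.

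**Step 4: power** from the noncentral t with the same SE and df, difference 0.5 SD, alpha 0.0125.

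| r | Narrowing before cost, 1−sqrt(1−r²) | Net narrowing | Half-width, SD (50/50) | Power at 50/50, 70/30, 80/20 | 50/(1−r²) per arm |
|---|---|---|---|---|---|
| no covariate | – | – | 0.509 | 48.5, 40.4, 29.8% | 50 |
| 0.2 | 2% | 1.5% | 0.502 | 49.9, 41.7, 30.8% | 52.1 |
| 0.3 | 5% | 4% | 0.488 | 52.6, 44.1, 32.8% | 54.9 |
| 0.5 | 13% | 13% | 0.443 | 62.8, 53.6, 40.6% | 66.7 |
| 0.7 | 29% | 28% | 0.366 | 82.3, 73.9, 59.6% | 98.0 |

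At r = 0.1 the net change is nil. At r = 0 the interval is about 0.5% wider. The last column is the number per arm that would give the same precision without the covariate, before its cost. The percentage narrowing does not depend on the iris split; the absolute half-widths and powers do.

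**Check.** 4,000 simulated data sets per setting, fitted with lens, iris and lens-by-iris, with and without baseline, gave mean half-widths at 50/50 of 0.507–0.509 SD unadjusted and 0.500, 0.488, 0.443 and 0.365 SD adjusted at r = 0.2, 0.3, 0.5 and 0.7.

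**The case against.** The strongest reply is that nothing is broken. The planned models give a valid randomized comparison, no section promises baseline adjustment, every hypothesis is labelled exploratory, and the sample size was not set to reach any power for eyestrain. SAP 1.4 leaves room for further analyses. All of that is true and limits this to an efficiency point. An analysis left to later discretion, however, is not a prespecified model.

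A second reply is that r is unknown and may be small. Baseline concerns whatever lens the subject habitually wore, follow-up concerns the assigned lens, and the Test lens has a variable shade, so the correlation could also differ by arm. This stands: at r of 0.2 or less the gain is negligible. With a common slope and equal arms, the r that applies is roughly the mean of the two arms. In simulation, 0.5 in Control with 0.1 in Test gave about 4% net narrowing, 0.5 with 0 about 3%, and 0.3 with 0 about 0.6%. These values lie within the range above, and none makes the covariate invalid or biases the estimate.

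Third, wear time is secondary and has no margin, so no decision rule depends on its interval width. That is fair, and it is why eyestrain carries the point.

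Finally, the score is derived by item response theory, and the SAP does not describe how the item parameters are set. A usable baseline needs the same parameters as follow-up, so the amendment has to say so.

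**Conclusion.** The point holds. Both Visit 1 values are collected before randomization, neither enters its model as covariate, response or change score, and no reason is given. The consequence is lost precision only: somewhere between nothing at r of about 0.1 and a 28% narrower interval at r = 0.7, with a penalty of about 0.5% if r is zero. For eyestrain, at 0.5 SD with an even iris split, that means power of 52.6 to 82.3% for r from 0.3 to 0.7, against 48.5% as planned. The correlation, effect size and iris split are all assumed. The documents do not show that the loss is larger for eyestrain than for wear time.

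The statement that no bias arises is confined to this omission. It does not cover other sources, such as the choice of analysis set: "Efficacy analyses will be performed on all randomized subjects who completed the study and did not substantially deviate from the protocol", analysed without imputation in the main analysis. The change is worth making because it is cheap and concerns a co-primary endpoint, but the planned analysis would be valid without it.

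**What to change.** Amend SAP 5.2.2 before the planned eyestrain interim analysis, so that the choice cannot be influenced by outcome data:

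- **Eyestrain:** add the Visit 1 eyestrain score as a fixed covariate, scored with the same item parameters as follow-up. A baseline-by-time term is optional.
- **Wear time:** add habitual wear time from Visit 1 as a fixed covariate.
- **Missing baseline:** state a simple rule that keeps those subjects in the model, such as mean imputation of the covariate only. Write it as an exception to SAP 5.1.2, which allows no imputation for the primary and secondary hypotheses beyond the multiple-imputation sensitivity analysis when dropout exceeds 15%.
- **Visual acuity:** no change. The Visit 1 ETDRS reading is taken on the assigned lens after randomization and must not be used as a baseline covariate.

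Change from baseline is not an equivalent remedy. With equal variances its variance ratio is 2(1−r), or 1.4, 1.0 and 0.6 at r = 0.3, 0.5 and 0.7, against 1−r² = 0.91, 0.75 and 0.51 for the covariate.

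Cost: a short amendment and no new data. It uses one degree of freedom per model, or four in the eyestrain model with baseline-by-time, and widens intervals by about 0.5% if baseline predicts nothing.
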